6.2 Randomization

Per Section 5.2 of the Study Protocol, randomization will be performed, using a 2:1 randomization ratio, with the strata defined as:

- investigational site,
- SOFA score (<6 versus ≥ 6)

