7.1 General Considerations

All safety analyses will be based on Safety Population; all efficacy analyses will be based on Modified Intent-to-Treat population, unless otherwise specified. Some specific sensitivity analyses of efficacy may be based on ITT and Per Protocol populations (for primary endpoints only). See Section 7.4 below for definitions of each analysis population.

All analyses will be considered as descriptive analyses. Derivation of two-sided 95% confidence intervals and p-values will be generated where applicable.

Time to event endpoints will be defined as the start date/time to the end date/time; censoring dates will be the last date/time the patient was determined to be event-free. Kaplan Meier methods will be used for time to event endpoint analyses; a log-rank test will be performed to compare the two survival curves. Timepoints estimates and median survival will be derived from the Kaplan Meier analysis. A Cox proportional hazards model may also be used to compare the two treatment arms using a hazard ratio.

Categorical endpoints will be calculated as the percentage of patients with the event, relative to the number of patients in a given analysis population (see Section 7.4). Stratified logistic regression approaches and/or repeated measures statistical approaches may be used to compare patients on the sargramostim and control arms, in addition to Fisher's Exact or Chi² tests (as appropriate). The randomization stratification factor for the baseline SOFA score (<6 versus \geq 6) will be considered for any stratified analysis.

Continuous endpoints will be summarized by n, means, medians, minimum, maximum, and 25th and 75th percentiles. Analysis of variance, analysis of covariance, and/or repeated measures statistical approaches may be used to compare patients on the sargramostim and control arms.

In the event that the underlying assumptions and/or distributions for a given statistical method are not satisfied, alternative statistical methods will be employed.

Additional exploratory analyses may be performed to evaluate the robustness and sensitivity of the study results, including but not limited to, additional evaluation of endpoints on other

analysis populations, subgroup analyses, treatment interactions, adjusted or stratified analyses, and/or alternative statistical methods.

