7.7 Demographics and Baseline Disease Characteristics

Demographic information for MITT Population will be summarized. The demographic data consists of age, gender, race, ethnicity, baseline height, body weight, body mass index (BMI), Body Surface Area (BSA). The baseline disease assessment scales, including the SOFA score (including categorization of <6 versus \geq 6), ordinal scale, and National Early Warning System 2 Score will be summarized. The baseline COVID-19 diagnostic information will also be summarized.

Individual demographics and other baseline factors will be listed by patient.

Continuous variables (for example, age, height, body weight, body mass index, body surface area, disease assessment scales) will be summarized by n, means, medians, minimum, maximum, and 25^{th} and 75^{th} percentiles. Number of patients and percentages will be used to describe categorical (discrete) variables (for example, gender, race, ethnicity and SOFA score <6 versus ≥ 6).

If there is a difference between the MITT and the Safety Population, the summary of baseline and disease characteristics may be repeated on the Safety Population.

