A Mixed Model Repeated Measures (MMRM) model will be used to evaluate the change in $P(A-a)O_2$ gradient, in which the change of $P(A-a)O_2$ gradient from baseline on each study day up to Day 6 (or day of discharge) will be included as dependent variable and treatment, study day (categorical), and treatment-by-study-day as fixed effects, patient as random effect, and the baseline value as a continuous covariate. An unstructured covariance matrix will be used for the MMRM analysis, unless the model does not converge, in which case the compound symmetry will be used. The change in $P(A-a)O_2$ gradient up to Day 6 will be evaluated by this MMRM model.

Change in oxygenation/respiratory parameter of P(A-a)O₂ gradient will also be presented by waterfall plot.

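### SOFA, a randomization stratum, is only optional in the SAP and is not written into the P(A-a)O₂, intubation, log-rank or mortality analyses

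*SAP*

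**What the plan says.** - **Randomization.** Section 6.2 names two strata: investigational site and "SOFA score (<6 versus ≥ 6" (the two SOFA groups). Section 7.7 already tabulates the two-level score at baseline.
- **P(A-a)O₂.** The model in Section 7.11.1.1 contains treatment, study day and "treatment-by-study-day as fixed effects, patient as random effect, and the baseline value as a continuous covariate". The ordinal-scale model in Section 7.11.2.1 has the same form. Neither has SOFA or site.
- **Intubation by Day 14.** Section 7.11.1.2 names Fisher's exact or a chi-square test and nothing else.
- **Mortality.** The Cox model in Section 7.11.2.2 has treatment arm alone. For time-to-event endpoints generally, Section 7.1 says "a log-rank test will be performed to compare the two survival curves", with no strata.
- **Where SOFA may enter.** Section 7.1 says that stratified logistic regression or repeated-measures approaches "may be used to compare patients on the sargramostim and control arms, in addition to" Fisher or chi-square tests for categorical endpoints, and that SOFA "will be considered for any stratified analysis". Section 7.11.1.1 gives a stratified logistic model in brackets as an alternative for the 10% change bins and the ≥33% improvement rate. Section 7.1 lists analysis of covariance for continuous endpoints without naming covariates. Its exploratory paragraph allows "subgroup analyses, treatment interactions, adjusted or stratified analyses, and/or alternative statistical methods".
- **Status of the results.** All analyses are descriptive, and Section 7.2 says the sample size rests on no hypothesis. Even so, "Derivation of two-sided 95% confidence intervals and p-values will be generated where applicable".

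**The concern.** A factor used to stratify randomization is normally carried into the analysis. Balancing the arms on SOFA reduces the true variance of the treatment comparison if SOFA predicts outcome. A model that omits SOFA does not credit this and reports a standard error that is too large. Here nothing commits any named primary or mortality analysis to SOFA, although the variable exists for every randomized patient. At stake are the width of the reported intervals and some power at a fixed 120 patients. Validity is not at stake.

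A smaller matter sits in the same section. The 10% change bins are ordered, but the tests named for them are chi-square and Fisher, which ignore the order.

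**Working it through.** The SAP gives no power, effect size, SD or event rate, so there is no figure to reproduce. From the SAP come 80 and 40 patients, 2:1 allocation and the SOFA strata. Every other input below is an assumption. Tests are two-sided at 5%.

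**1. P(A-a)O₂, single time point, in closed form.** Let R² be the share of variance remaining after the baseline gradient that SOFA explains, and let the true difference be 0.5 SD.
- Reported SE without SOFA: √(1/80 + 1/40) = 0.194 SD. With SOFA: 0.194 × √(1 − R²).
- With exact SOFA balance, the true SE is the smaller one in both cases. The unadjusted test therefore has size 2Φ(−1.96/√(1 − R²)) and power Φ((0.5/0.194 − 1.96)/√(1 − R²)). The adjusted test has size 5% and power Φ(0.5/(0.194√(1 − R²)) − 1.96).

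| R² | SE excess, unadjusted | Size, unadjusted | Power, unadjusted | Power, adjusted |
|---|---|---|---|---|
| 0 | 0% | 5.0% | 73.3% | 73.3% |
| 0.05 | 2.6% | 4.4% | 73.8% | 75.5% |
| 0.10 | 5.4% | 3.9% | 74.4% | 77.7% |
| 0.20 | 11.8% | 2.8% | 75.7% | 82.3% |

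The gains are about 0, 2, 3 and 7 points. Simulation with blocks of 6 within SOFA strata and 10–30% of patients at SOFA ≥6 agrees. At R² = 0.10, power is 72.9–73.1% against 75.8–76.5%. At R² = 0 the SE is 0.194 either way. A simulation of the six-day repeated-measures model (40% at SOFA ≥6, R² = 0.10) gave 71% against 74%, with the unadjusted SE 5.3% larger.

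**2. Day 14 intubation, conditional odds ratio 0.35, chi-square against Cochran-Mantel-Haenszel (CMH) by SOFA.** Risks are control risks for SOFA <6 / ≥6.
- 20/20%: gain 0.1 points. 20/40%: 1.1–1.5. 10/40%: 3.4–3.5 (all with 20–40% at SOFA ≥6).
- 20/50%: about 2–3 points. 20/70%: about 5–10 (with 10–30% at SOFA ≥6).
- Blocking within 15 assumed sites by SOFA, risks 10/40%: the gain falls from 3.9 to 2.0 points with 20% at SOFA ≥6, and from 2.5 to 1.0 with 10%. At 20/40% with site blocking it is −0.2 to 0.6.
- Under no effect, chi-square at 20/50–70% rejects in 2.4–4.4% of trials and CMH in 4.8–5.2%.

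**3. Response of ≥33%, odds ratio 2.5, chi-square against CMH.** Rates are control rates for SOFA <6 / ≥6.
- With 40% at SOFA ≥6: 61.8 against 61.9% (30/30%), 57.6 against 61.4% (40/20%) and 45.8 against 54.4% (45/10%).
- With 10% at SOFA ≥6, the last two gains fall to 0.8 and 2.9 points.

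**4. Mortality, log-rank against stratified log-rank.**
- Treatment HR 0.5, 35% control mortality at Day 90, 40% at SOFA ≥6: 48.8 against 48.7% (SOFA HR 1), 47.2 against 48.3% (HR 2) and 43.3 against 49.4% (HR 4).
- Treatment HR 0.45, 20–30% at SOFA ≥6: gains of 0.4–0.7 points at SOFA HR 2 and 4.6–4.9 at HR 4, with on average 18–38 deaths per trial across the null and alternative settings.

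**5. What adjustment changes in the ratios.** Take 20% at SOFA ≥6, control risks 20/70% and conditional odds ratio 0.35. Treated risk is 0.8 × 0.0805 + 0.2 × 0.4495 = 0.154, and control risk is 0.8 × 0.20 + 0.2 × 0.70 = 0.30. The marginal odds ratio is (0.154/0.846)/(0.30/0.70) = 0.43. The adjusted and unadjusted analyses therefore estimate different quantities.

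**6. Ordered bins, assumed SD 35 points, chi-square against Wilcoxon.** Power is 9 against 38% for a 12-point shift, 25 against 70% for 18 points and 30 against 78% for 20 points. In the 12- and 18-point runs, about 57–58% of expected cell counts are below 5.

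**The case against.** The strongest reply is that nothing here is an error. The analyses are declared descriptive, no power target exists to be missed, and leaving SOFA out errs on the safe side. All of that stands, and it limits the weight of the point. It does not remove it, because intervals and p-values will be reported and their precision matters.

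The SAP also does not ignore SOFA. Stratified logistic regression is permitted for categorical endpoints generally, which covers intubation, and it is a bracketed option for the P(A-a)O₂ categories. A reader might infer that SOFA is missing from the analysis altogether, and the text does not support that. The accurate statement is that its use is optional and unfixed. Fisher or chi-square is likewise left open for intubation.

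The gain may also be small. SOFA has a respiratory component (Section 7.11.3.2), and the P(A-a)O₂ model already adjusts for the baseline gradient, so the R² = 0.20 row may be optimistic. With 10% at SOFA ≥6 there would be about 12 such patients, 8 and 4 by arm. Blocking within site reduces the intubation gain further. These reservations stand.

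Finally, the bins feed one supplementary p-value. The same data are modelled as a continuous change and shown in a waterfall plot.

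**Conclusion.** The point holds as a modest improvement. SOFA stratifies the randomization but is not written into the P(A-a)O₂ model, the Day 14 intubation test, the log-rank test or the mortality Cox model, and elsewhere it is optional.

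The gain from adjusting runs from about zero to several power points. It depends on SOFA's prognostic strength, the share of patients at SOFA ≥6 and the blocking, none of which the SAP gives.

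Three stronger readings should be resisted:
- **Inflated false-positive error.** Omitting SOFA makes the tests conservative. Even taking the smallest p-value of the three tests listed for ≥33% response gave 5.0–5.2% under no effect.
- **An underpowered trial.** The SAP claims no power.
- **Adjustment that is free everywhere.** That holds for the linear models only. For odds and hazard ratios the target becomes conditional on SOFA, and strata may be sparse.

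The ordered-bin point is correct but minor. Its power difference is large under the assumed SD, but it touches only a supportive tabulation.

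**What to change.** 1. Add the SOFA stratum as a fixed effect in the P(A-a)O₂ model (Section 7.11.1.1) and in the ordinal-scale model (Section 7.11.2.1). This costs one parameter and, in the simulations, no visible precision when SOFA is not prognostic.
2. Make CMH or SOFA-adjusted logistic regression the stated analysis for Day 14 intubation and for ≥33% response, replacing the bracketed alternative. Keep Fisher or chi-square as supportive.
3. Stratify the mortality log-rank and Cox analyses by SOFA, and keep the unstratified results as supportive.
4. Label adjusted odds and hazard ratios as conditional on SOFA, and say what is done if a stratum is too sparse.
5. State that site is not adjusted for, or how it is handled.
6. Minor: compare the 10% bins with a Wilcoxon, van Elteren or trend test.

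The cost is SAP wording only. No new data are needed, because the stratum was required to randomize each patient. The price is the change of target in items 2 and 3, which the supportive unadjusted results make visible.

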7.1.5 Missing Data Handling

In general, no imputation of missing data is planned for the primary analyses. However, for purposes of any sensitivity analyses, missing data may be imputed using last-observation-carried forward, or other advanced statistical imputation methods.

For the efficacy analyses based on oxygenation parameters, up to Day 6, if the assessment on Day 6 is not available, then the last prior non-missing value, after baseline will be used. See Sections 7.1.2, 7.1.3, and 7.1.4 for algorithm on determining assessments to be used for analysis.

Imputation for P(A-a)O₂ gradient, intubation rate and ordinal scale will not be performed.

If using last observation carried forward, a missing follow-up visit value will be imputed as that patient's previously observed value.

In the absence of any other specifications, the following rule will be used for missing time-toevent data:

• Patients who are alive (not lost to follow up) and did not experience the event of interest will be censored at the date last known to be alive and to be event-free.

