7.11.1 Primary Efficacy Evaluations

For primary efficacy measures based on oxygenation parameters, the main timepoints of interest for analyses are baseline, up to Day 6 for P(A-a)O₂ gradient, and by Day 14 for rate of intubation, where data are available, unless otherwise specified.

See Sections 7.1.2, 7.1.3, and 7.1.4 for algorithm on determining assessments to be used for analysis.

As ABG was required only at baseline and at Day 6/Post-Treatment visit (or day of discharge if earlier), the number of patients with complete data at all study visit days is expected to quite limited. Therefore, the primary timepoint for analyses for data based on ABG will be up to Day 6.

7.11.1.1 Oxygenation Up to Day 6

The $P(A-a)O_2$ gradient will be derived using arterial blood gas assessment via arterial puncture at baseline and up to Day 6, or day of discharge whichever is earlier. See Sections 7.1.2, 7.1.3, and 7.1.4 for algorithm on determining assessments to be used for analysis.

The change from baseline and percentage from baseline is defined as:

Percentage Change from Baseline= Change from Baseline/ Baseline

The P(A-a)O₂ gradient, the percent change from baseline up to Day 6 will be tabulated based on "unchanged or deteriorated" [no difference or positive percent change from baseline] and "improved" [negative percent changer from baseline] by 10% change increments. In addition,

the percentage of patients with $a \ge 33\%$ improvement for each treatment arm will be provided. For both of these analyses, a Chi-square, or Fisher's exact test (or stratified logistic model) will be generated to compare the treatment arms. Alternative cutoffs for defining meaningful improvement may be used (e.g., 25%, 50%), with similar analyses methods as above.

The maximum change from baseline and maximum percentage change from baseline will be summarized up to Day 6, and for the study duration.

Maximum percentage change from baseline is defined as:

Maximum Percentage Change from Baseline= Maximum Change from Baseline/ Baseline

For these analyses, the baseline is defined as the last available assessment prior to administration of study drug (see Section 7.1.2 above). Except as noted in Section 7.1.1, unscheduled records will be excluded from the summaries at specific timepoints but will be included in the maximum change from baseline.

A listing of all P(A-a)O₂ gradient measurements will be provided.

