7.11.2 Secondary Efficacy Evaluations

For secondary efficacy measures. the main timepoints of interest for analyses are baseline, Days 6, 14, 28, where data is available, unless otherwise specified.

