7.11.2.1 Change in Ordinal Scale

Ordinal scale will be assessed at the Screening/Baseline, during the 5 days of treatment administration, and at any days where the patients are hospitalized through Day 28 and at Day 90. Baseline for the following analyses is defined as the last ordinal scale prior to administration of study drug. The number of patients with an improvement in the ordinal scale, defined as a change from baseline of ≥ 2 points, will be tabulated.

A MMRM model will be used to evaluate the change in ordinal scale, in which the change of ordinal scale from baseline on each timepoint of interest will be included as dependent variable and treatment, timepoint (categorical), and treatment-by-timepoint as fixed effects, patient as random effect, and the baseline value as a continuous covariate. An unstructured covariance matrix will be used for the MMRM analysis, unless the model does not converge, in which case the compound symmetry will be used.

Descriptive statistics for the overall treatment effect based on the MMRM model will include the least-squares (LS) mean difference, LS mean change from baseline for each treatment arm, their corresponding 95% CIs, and the p-values associated with the treatment difference compared to SOC. In addition, LS Means for the treatment differences at each timepoint of interest between treatment arms may also be provided with the same set of statistics derived from the same MMRM model defined above based on the MMRM estimates.

Additionally, the non-model based descriptive statistics for the corresponding change from baseline (overall) in the ordinal scale at each visit or timepoint of interest, change from baseline and maximum change from baseline will be evaluated and summarized by treatment arm. Except as noted in Section 7.1.1, unscheduled records will be excluded from the summaries at specific timepoints but will be included in the maximum change from baseline.

All available values of the ordinal scale, including change from baseline and maximum change from baseline will be listed by arm and patient. Refer to Appendix C of the Study Protocol for the ordinal scale categories.

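### Both MMRMs carry a redundant random patient effect, and their only fallback, compound symmetry without a robust SE, can misstate per-timepoint standard errors in either direction

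*SAP*

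**What the plan says.** SAP 7.11.1.1 models the change in P(A-a)O2 gradient "from baseline on each study day up to Day 6 (or day of discharge) will be included as dependent variable". Treatment, categorical study day and their interaction are fixed effects. The model also has "patient as random effect, and the baseline value as a continuous covariate. An unstructured covariance matrix will be used for the MMRM analysis". One fallback is given: "unless the model does not converge, in which case the compound symmetry will be used".

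SAP 7.11.2.1 repeats this design for the ordinal scale, again with "patient as random effect, and the baseline value as a continuous covariate", an unstructured matrix and compound symmetry as the only fallback. For secondary measures, 7.11.2 states that "the main timepoints of interest for analyses are baseline, Days 6, 14, 28, where data is available, unless otherwise specified".

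On data availability, 7.11.1 says "As ABG was required only at baseline and at Day 6/Post-Treatment visit (or day of discharge if earlier"), and that "the number of patients with complete data at all study visit days is expected to quite limited". Section 7.1.5 adds: "Imputation for P(A-a)O₂ gradient, intubation rate and ordinal scale will not be performed". The rule there that takes the last earlier post-baseline value serves the Day 6 evaluation and does not supply the missing early days.

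Neither MMRM section names a robust standard error, a degrees-of-freedom method or an intermediate covariance structure. Sections 7.1 and 7.2 call all analyses descriptive, and 7.1 still provides for 95% confidence intervals and p-values.

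**The concern.** There are two linked problems.

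- **The specification is over-parameterised if taken at its word.** A random patient intercept adds the same constant to every element of the within-patient covariance matrix. An unstructured matrix can already absorb that constant, so the two cannot be told apart. One programmer will fit both terms. Another will read the phrase as naming the subject on whom measurements are repeated. What the first sees depends on the software: a zero patient variance, a warning, or a failure to converge.
- **The only consequence the SAP attaches to non-convergence is a move to compound symmetry.** That structure forces one variance on all days and one correlation on all pairs of days. If the spread of the change scores differs between days, a single-day contrast gets a standard error based on the average variance, not on that day's variance.

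At stake are the confidence intervals and p-values reported for the Day 6 P(A-a)O2 difference and for any per-timepoint ordinal-scale differences.

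**Working it through.** **Inputs.** From the SAP: 80 v 40 patients (7.2), the covariance wording and fallback (7.11.1.1, 7.11.2.1), and the blood-gas schedule (7.11.1). The SAP gives no SD, correlation, power or effect size, so there is no figure of its own to reproduce. The SDs, correlations and missingness below are assumptions.

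**Step 1: redundancy.** The implied total covariance is V = s²J + R, where s² is the patient variance, J the matrix of ones and R unstructured. For any c that keeps it positive definite, replacing R by R + cJ and s² by s² − c leaves V unchanged. R has T(T+1)/2 parameters for T timepoints.

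| Timepoints | Unstructured alone | With random intercept | Rank |
|---|---|---|---|
| 3 | 6 | 7 | 6 |
| 5 | 15 | 16 | 15 |
| 6 | 21 | 22 | 21 |

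Compound symmetry plus a random intercept is redundant too: 3 parameters, rank 2.

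**Step 2: does the redundancy move the result?** On one simulated 80:40 data set, one fixed V was split four ways (s² = 0, 824, 1647, 2608). Every split gave REML log-likelihood −3104.237, Day 6 estimate −6.225 and SE 24.177. Only the split is undetermined. The treatment effect and its SE are not affected.

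**Step 3: how fragile is the unstructured fit for P(A-a)O2?** If a proportion q of patients has a blood gas on any given early day, independently between days, the number with both of two given early days is 120q². For q = 0.5 this is 30. For q = 0.15 it is 2.7, with 40 × 0.15 = 6 control patients per day. Covariances between early days would then rest on very few patients, with or without the random effect.

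**Step 4: SE under compound symmetry, complete data.** The true SE at day t is √[V_tt(1/80 + 1/40)] = 0.1936 × SD_t. The fitted common variance is about the mean of the V_tt, so the ratio of model SE to true SE at the last day is √(mean variance / last variance). The implied rejection rate at nominal 5% is 2[1 − Φ(1.96 × ratio)].

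- SDs 1.0, 1.1, …, 1.5: √(1.592/2.25) = 0.841, about 10%.
- SDs 1.0, 1.2, …, 2.0: √(2.367/4) = 0.769, about 13%.
- Ordinal scale at three timepoints, SDs 1.0/1.5/2.0: Day 28 √(2.417/4) = 0.777, about 13%; Day 6 √(2.417/1) = 1.555, so there the SE is too large.

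Simulation without a treatment effect (8,000 trials, AR(1) correlation 0.7, complete data) agrees for the two six-day cases: 9.8% and 12.9% under compound symmetry, against 5.0% and 4.8% under an unstructured matrix.

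**Step 5: range at Day 6.** Large-sample calculation, AR(1) 0.7, six days. In the last two columns Day 6 is observed in 85%. Entries are model SE / true SE, with the rejection rate at nominal 5%.

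| Assumed SD, Day 1 to Day 6 | All days complete | Early days 50% | Early days 15% |
|---|---|---|---|
| 100 throughout | 1.00 (5.0%) | 0.99 (5.2%) | 1.00 (5.0%) |
| 80 to 120 | 0.84 (9.9%) | 0.86 (9.4%) | 0.92 (7.2%) |
| 60 to 120 | 0.77 (13.2%) | 0.79 (11.9%) | 0.88 (8.3%) |
| 120 to 80 | 1.26 (1.3%) | 1.22 (1.7%) | 1.15 (2.5%) |

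For the average over all days the ratio is 1.00 in every scenario with complete data. With sparse early days it runs from 0.87 to 1.18.

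**The case against.** **The redundancy is harmless in itself.** This stands, as step 2 shows. A reader might infer that the model cannot give a unique treatment effect, or that its wording alone will push the analysis to compound symmetry. The documents support neither. The trigger in the SAP is failure to converge, and a singular Hessian or a covariance-matrix warning is not the same thing. In a small test the redundant model was fitted to six simulated data sets, three complete and three with half of Days 1-5 missing. All six fits converged and matched the plain unstructured fit to within 0.0001. That was one optimiser, so it does not exclude failure elsewhere, but it rules out treating failure as certain.

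**The phrase may only identify the repeated-measures subject.** This is a fair reading, since each section names a single covariance matrix. The SAP does not say so, and if that is the intent one sentence settles it.

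**Compound symmetry is not always anti-conservative.** This also stands. A reader might infer that its intervals are always too narrow. With equal SDs they are about right, and with falling SDs too wide.

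**Per-timepoint contrasts are not always the committed summary.** For the ordinal scale, 7.11.2.1 commits to the overall effect and makes timepoint differences optional; the overall contrast is little affected with complete data. For P(A-a)O2 the SAP does not name the contrast, but 7.11.1 makes the period up to Day 6 the primary timepoint, so a Day 6 contrast is a natural choice.

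**The analyses are descriptive, and 7.1 allows other methods if assumptions fail.** The first half lowers the stakes but does not remove them, because intervals and p-values will be reported. The second half names no method, so the choice would be left until the data have been seen.

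**Conclusion.** The point holds as a matter of specification and of a weak fallback rule. The random patient effect is redundant beside an unstructured matrix. It does not bias the treatment estimate or its SE, but what the software does with it is unpredictable. For P(A-a)O2, the documented reason to expect trouble with the unstructured fit is the sparse Day 1-5 blood-gas data, which deleting the random effect would not cure.

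If the fallback is used, the Day 6 SE could be about 16-23% too small under SDs that rise 1.5- to 2-fold with complete data (8-12% with early days at 15%), about right under equal SDs, and 15-26% too large under SDs falling from 120 to 80. Size and direction both rest on assumed SDs, correlation and missingness.

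No confirmatory error rate is at stake, because the SAP sets no alpha or decision rule. The correction is worth making before database lock, but the planned analysis is not invalid without it. The common baseline slope across days is a legitimate prespecified choice and not part of the fault.

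**What to change.** In 7.11.1.1 and 7.11.2.1:

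1. Delete the random patient effect, or state that patient only identifies the subject on whom measurements are repeated.
2. Keep the unstructured residual matrix, and specify REML with Kenward-Roger degrees of freedom.
3. Replace the single fallback by a fixed order: heterogeneous Toeplitz, heterogeneous AR(1), then compound symmetry last and only with empirical (sandwich) standard errors. Kenward-Roger adjusts model-based SEs, so give the sandwich step its own degrees-of-freedom rule.
4. Say what counts as non-convergence, so that a warning alone does not decide the structure.

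A baseline-by-day interaction is optional.

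Cost: SAP wording, slightly more programming, and possibly wider intervals if a fallback is used. No new data are needed.
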